D5.2 EHR variable construction: EHR measures are listed in Table 5. Monthly EHR sums will be averaged by quarter and by year. If categorical variables change over an aggregated time point, the most consistent designation over the analyzed epoch will be used.

Health Services Utilization
Outpatient Visits (any service)
Outpatient Visits (MH service)
Emergency or Urgent Care Visits
Inpatient MH
Inpatient (any service)
Pharmaceutical Utilization
Antidepressant
Antipsychotic
Mood Stabilizer
Anxiolytics
Other medications (non-psychiatric)
Change in Pharmaceutical
Antidepressant
Antipsychotic
Mood Stabilizer
Anxiolytics
Other medications (non-psychiatric)
Mental Health (Current and Lifetime)
Depression
Bipolar disorder
Schizophrenia or schizoaffective disorder
Generalized Anxiety Disorder
Posttraumatic Stress Disorder
Specific Phobia
Panic Disorder
Social Phobia
Personality Disorder
ADHD
SUD
Gambling Disorder
Eating Disorders
Suicidality

Table 5. EHR data extracted at baseline and follow-

E. DATA ANALYSIS

E1. Design and Sample Size

This is a single-site, two-arm RCT with individual participant urn randomization. We propose to randomize 130 Veterans. Approximately 65 will be randomized to active TMS+BCBT and 65 participants will be randomized to sham TMS+BCBT. Recruitment for the intervention will cease once randomization goals are met (i.e. n= ~65 Veterans per condition). Additionally, we will be enrolling 60 Veterans, who will be matched on age (within 5 years), primary psychiatric diagnosis, and sex, for a total of 190 Veterans to be enrolled. A subsample of these veterans (120 in total; one group (n=30) with suicide ideation and another group (n=30) with suicide attempts; and controls (n=60) will be used in the analyses of brain-based biomarkers for suicidality. Veterans will be assessed at the study timepoints outlined in C3. Assessments.

E1.1 Overall Analytic Approach across Aims

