E2.2.1 Statistical power and sample size for our primary outcome: With 65 persons per group, Lehr's equation [73] instructs that minimum detectable standardized mean difference effect size difference (d) between treatment groups at the baseline assessment is $\text{sqrt}(16/n)$, where n is the per-group sample size, or 0.50 standard deviation units, a medium effect size in Cohen's effect size taxonomy [74]. Given the ANCOVA design, we will be able to detect a smaller effect depending upon the magnitude of the pre-post correlation (r) of the suicidal behavior composite outcome $\{d = \text{sqrt}([16(1-r^2)]/n)\}$, which under the assumption of a moderate correlation (r = .2) the minimum detectable effect size is $d = .47$. These are medium or typical effect size magnitudes [75] and are likely to describe effects of minimal clinical significance or practical importance. Of note, these are also comparable with prior TMS studies [64,65] who described effect sizes of .5-.52, and more recent studies indicating larger (d=.9) effect sizes of TMS used with medications [76]. While we recognize these are effect sizes for depressive symptoms, in our pilot work we found reduction in depressive and suicide-related symptoms to be highly correlated. For our secondary outcome, we used simulations to determine the minimum detectable difference. If we assume that 21% of the sample will experience a suicide attempt over 12 months follow-up, if the cumulative risk of suicide attempt is 4.5% over 12 months in the TMS+BCBT group (hazard ratio = 0.19) we

will have 81.1% power to detect such an effect using a type-I error rate of 5% in a Cox proportional hazards model framework.

E2.3 Secondary hypotheses

For this aim we hypothesize, compared to sham TMS+BCBT, Veterans who receive active TMS+BCBT will have superior improvements in psychosocial functioning and fewer psychiatric hospitalizations/crisis visits during the follow-up period. The outcomes for this aim are a)

WHODAS score b) number of psychiatric hospitalizations/crisis visits c) reduced suicide ideation as measured by the C-SSRS. The analysis for the psychosocial functioning outcome, (a), and the suicidal ideation severity score from the C-SSRS, (c), will be a repeated measures ANCOVA, as with the primary hypothesis, using a generalized linear mixed effect model. For part (b), the outcome will be a count variable, for which we will use negative binomial regression.

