E2.3.1 Statistical power and sample size considerations: Sample size considerations for part

(a) are similar to the primary hypothesis, and the minimum detectable effect size difference is a standardized mean difference of 0.5SD units. Without pilot data on the number of hospitalizations/crisis visits, it is difficult to forecast the distribution and detectable difference in distribution on the count outcome (part b). Rules of thumb provided by Van Belle [77] suggest we will be able to detect a relative rate of $\exp(4/\sqrt{n})$, where n is the per-group sample size, or a reduction in the rate of hospitalizations of about 61% or more among those receiving active TMS+BCBT plus versus sham.

E2.4 Moderator and mediator effects

In addition to the above hypotheses, we will conduct exploratory latent growth curve analyses to compare the trajectory of change for primary, secondary, and tertiary outcomes (i.e. linear ascending, descending, or quadratic) between sham TMS+BCBT versus active TMS+BCBT. We will include moderator variables in these models (e.g. diagnosis, comorbidity, gender), which may identify patients who will benefit more or less to the addition of active TMS+BCBT versus sham TMS+BCBT. We also will investigate mediating variables to determine the mechanisms through which TMS produces its effects on clinical outcomes. The set of analyses in this aim are motivated by [78], who suggest exploratory, hypothesis generating analyses be conducted after primary study aims are addressed to attempt to decide for which sample sub-groups the intervention might be more efficacious or have more lasting effects. The analytic approach will be like that described for the primary and secondary aims, although in addition to the timepoint effect indicators, we will examine models with more parsimonious time structure (e.g., linear, piecewise linear, negative exponential) and then attempt to describe factors that predict variations in important components of the implied change trajectory. We will make use of generalized linear mixed effect models and compare alternative time bases using information criteria before adding covariates, mediators, and moderators. Treatment effect mediation will be evaluated by comparing treatment effects estimated before and after adjusting for the main effect of putative mediators. Moderation effects will be examined as three-way interactions of the putative moderator, treatment assignment, and time.

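### Two stated detectable effects do not follow from the plan's own formulas: the hospitalisation rule gives a 39% reduction, not 61%, and r = .2 gives d = .49, not .47 (minor)

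*Combined protocol and SAP*

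**What the plan says.** Section E1 sets the size: "Approximately 65 will be randomized to active TMS+BCBT and 65 participants will be randomized to sham TMS+BCBT". Section E2.2.1 works from the same 65 per group. It gives an unadjusted detectable difference of √(16/n), stated as 0.50 SD. It then says that the baseline-adjusted analysis can detect something smaller, "depending upon the magnitude of the pre-post correlation (r) of the suicidal behavior composite outcome", by d = √(16(1 − r²)/n). The result is stated thus: "under the assumption of a moderate correlation (r = .2) the minimum detectable effect size is" .47.

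For hospitalisations and crisis visits, section E2.3 says that "the outcome will be a count variable, for which we will use negative binomial regression". Section E2.3.1 concedes: "Without pilot data on the number of hospitalizations/crisis visits, it is difficult to forecast the distribution and detectable difference". It then turns to a published rule of thumb, under which "we will be able to detect a relative rate of" exp(4/√n), n being the per-group size, and equates this with "a reduction in the rate of hospitalizations of about 61% or more among those receiving active TMS+BCBT".

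**The concern.** Both sections print a formula, its inputs and a result, so a reader can repeat the calculation, and in both cases gets a different answer. For hospitalisations the gap is 39% against 61%, too wide for rounding. For the primary outcome it is small, but the stated r and d cannot both be right.

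These are the plan's stated detectable effects for the primary outcome and a named secondary outcome, and a null result may well be judged against them. There is a second hazard. Someone who notices the hospitalisation slip and simply substitutes 39% would present, as the trial's sensitivity, a figure that takes no account of how often events occur or how unevenly they are spread.

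**Working it through.** **Inputs from the documents.** n = 65 per group (E1, E2.2.1); r = .2 and d = .47 (E2.2.1); the rule exp(4/√n) and the 61% reduction (E2.3.1).

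**Check that n and the factor 16 are understood.** √(16/65) = 0.496, which rounds to the stated 0.50. The unadjusted figure is correct.

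**Hospitalisation rule**
- √65 = 8.062; exp(4/8.062) = 1.642; 1/1.642 = 0.609.
- Reduction = 1 − 0.609 = 0.391, about 39%.
- Solving the rule for n at a rate ratio of 0.61: (4/ln(1/0.61))² = 65.5, the trial's own size.
- Solving for n at a true 61% reduction (rate ratio 0.39): (4/ln(1/0.39))² = 18.0 per group.
- Other sizes do not rescue the figure: the reduction is 50.7% at n = 32, 40.3% at 60, 39.3% at 64 and 29.6% at 130. Reading 1.64 as an increase gives 64%, not 61%.

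The printed 61% is therefore the rate ratio, 0.609, reported as a reduction.

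**Adjusted primary effect**
- r = .2: √(16 × 0.96/65) = 0.486, which rounds to .49.
- r = .3: √(16 × 0.91/65) = 0.473, which rounds to .47.
- To two decimals, r from .29 (0.4748) to .34 (0.4666) rounds to .47; .28 (0.4763) and .35 (0.4648) do not.
- Keeping r = .2, d = .47 would need 16 × 0.96/0.47² = 69.5, about 70 per group.
- Variants at r = .2, taking 80% power where a power is needed: exact multiplier in place of 16, 0.482; the same at alpha 0.049, 0.483; noncentral t, 0.485; one-sided, 0.427; (1 − r) for (1 − r²), 0.444; change score, 0.628. None gives .47.
- Power by a two-group noncentral t with residual SD √(1 − r²), 65 per group, two-sided .05: at r = .2, 77.5% for d = .47 and 80.1% for d = .486; at r = .3, 79.6% for d = .47.

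**How far the rule's 39% can be trusted.** The documents give no event rate or dispersion, so everything below rests on assumed inputs. Let μ be the sham mean count per person, k the negative binomial dispersion and RR the rate ratio. The detectable reduction is the smallest for which −ln(RR) ≥ 1.96√V₀ + 0.84√V₁. Here V₁ = (1/μ + 1/(μ·RR) + 2k)/65, and V₀ is the same quantity with both arms at their average rate.

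| Assumed k | μ = 0.25 | μ = 0.5 | μ = 1 | μ = 2 |
|---|---|---|---|---|
| 0 | 73% | 57% | 43% | 32% |
| 1 | 76% | 63% | 54% | 47% |
| 2 | 79% | 68% | 60% | 56% |

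These are approximate. Simulated negative binomial regression at the k = 1 reductions gave power of 74.6%, 77.7%, 78.9% and 77.7% (1,000 trials each; the 3–5% of fits that failed at μ = 0.25 were excluded), so that row is if anything slightly too small. The grid falls on both sides of 39%.

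**The case against.** The best defence is that E2.3.1 already hedges: it says there are no pilot data and presents the figure as what a rule of thumb suggests. It can be added that 61% may be nearer the truth than 39%. In the grid, an assumed sham mean of 0.5 with dispersion 1 gives 63%. Both points are fair, but neither removes the error. Choosing a rule is an approximation; once the rule and n are fixed, so is its output, and the plan attributes 61% to the rule. Any agreement with a fuller calculation is accidental. What the existing hedge lacks is a statement that the rule uses neither event rate nor dispersion.

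One might also read the sentence as a reduction to 61% of the sham rate. The words about 61% or more then point the wrong way, since larger effects would leave less than 61%.

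On the primary outcome, the gap is 0.016 SD in a formula offered as approximate, and the effect is medium-sized at .47 or .49. The power figures above also describe a single two-group comparison at .05, whereas section E2 plans repeated measures and a final level of 0.049. That stands, and is why this is minor.

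Three stronger readings are tempting, and the documents support none of them:
- A reader might infer that the trial can in fact detect a 39% reduction. That is the rule's output only; no event rate or dispersion is given to support it.
- A reader might infer that the detectable reduction must exceed 39%. With an assumed mean of 2 and no overdispersion it is about 32%.
- A reader might infer that the sponsor overstated primary power. That would need d to be the misprint; if r was meant to be about .3, d = .47 is consistent, and the documents do not show which was intended.

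**Conclusion.** Both figures are wrong as written, and the matter is minor. The hospitalisation rule with 65 per group gives a rate ratio of about 0.61, a reduction of about 39%, where the plan prints 61%. The slip is conservative relative to the rule, because it claims less sensitivity than the rule allows. For the primary outcome, r = .2 and d = .47 do not agree: the formula gives .486 at r = .2. The difference is worth under 3 points of power on the simple calculation.

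The arithmetic rests only on the plan's formulas and its 65 per group. The power comparison also assumes one follow-up comparison and two-sided .05. The grid rests on assumed means and dispersions, and shows only that the rule's figure could be materially off, in either direction. Neither slip alters enrolment or the planned analyses.

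**What to change.** **Section E2.3.1.** Replace the 61% clause with: a rate ratio of about 0.61 (a reduction of about 39%); this is the output of the rule only, which takes no account of the event rate or of overdispersion, so under the planned negative binomial model the detectable reduction may differ materially, and could be considerably larger if events are few or overdispersed. Keep the caveat in the same sentence, since the corrected number looks more favourable. The protocol need not print a range built on assumed inputs. If an illustration is wanted, show the whole grid (about 32% to 79% for sham means of 2 to 0.25 and dispersion of 0 to 2), labelled as assumed and approximate.

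**Section E2.2.1.** Either restate d as .49 at r = .2, or state and justify r of about .3 for d = .47. Leave the unadjusted 0.50 as it is.

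The cost is two sentences of text, with no change to sample size, outcomes or analysis.

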E2.4.1 Statistical power and sample size considerations: As we view tertiary analyses as exploratory and hypothesis generating, we do not present a priori specified sample size or minimum detectable effect size statistics. We have no doubt that we may be underpowered to detect all but large moderation effects. Our inferences will be made cautiously and be guided

by confidence intervals obtained by bootstrap resampling of the observed data.

E3. Aim 2 Analytical Plan (Analyses Related to Cognition and Neuroimaging)

All de-identified data from this study for Aim 2 will be combined with data from subjects who completed neuroimaging procedures in PVAMC IRB protocol #2018-051.

E3.1 Evaluate the relationship between STBs and reward circuits involved in decision-making in Veterans.

Hypothesis: Neural and behavioral correlates of decision-making will differentiate Veterans with STBs from those without STBs.

Rationale: Suicidality is associated with maladaptive decision-making. Neuroimaging in non-Veterans has shown that STBs are accompanied by functional and anatomical differences in the striatal-to-VMPFC reward circuit implicated in decision-making. It is unknown if these potential neurocognitive markers of suicide generalize to Veterans.

Between-group contrasts of decision-making, structural MRI, and functional MRI will be used to test our hypothesis.

E5.1 Participant groups: The STB group will be comprised of Veterans hospitalized for suicide attempt (up to n=30) or suicidal ideation (up to n=30). The diagnosis matched control group is comprised of Veterans (up to n=60) without current STBs. Per power estimations computed with G Power software⁴², 85% power to detect a medium-sized effect of group (0.4) in an ANCOVA model with three groups and two covariates is afforded by a total sample size of 72, or n=24 participants per group. Our enrollment targets exceed this estimate to account for loss of participants that are unable to complete all aspects of the study.

Data sources: Decision-making tasks include the scanned reward expectancy task (card guessing), and the un-scanned Iowa Gambling and Monetary Choice (Delay Discounting) tasks. Structural MRI and diffusion MRI data. FMRI data used in Aim 1 analyses will come from either the card guessing reward task or resting state functional MRI runs.

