General statistical details: Age and sex will be treated as covariates of no interest in all statistical analyses. Intracranial volume (computed by Freesurfer) will also be used as a nuisance covariate in morphometry analyses to control for size-related variance. Residual effects of motion on functional connectivity estimates will be tested post hoc by regressing individuals' frame-to- frame motion against

functional connectivity beta values ⁵⁵. Potential effects of impulsivity, depression, anxiety, and sleep on outcomes will be explored in post hoc sensitivity analyses.

Behavioral Data Analysis:

PhenX Toolbox Monetary-Choice Questionnaire⁴³: The protocol is scored by calculating where the respondent's answers place him or her amid reference discounting curves; placement amid steeper curves indicates higher levels of impulsivity. Subject-specific discounting rates will be entered into MATLAB ANCOVA models testing group differences.

PhenX Toolbox The Iowa Gambling Test^{TM 4}: Total winnings and the ratio of high vs. low risk gambles will be entered into MATLAB ANCOVA models testing group differences.

MRI Analyses: Analyses for primary hypothesis testing will employ a region of interest (ROI) approach. ROIs in VMPFC, orbitofrontal cortex, and the striatum will be used in structural and functional neuroimaging analyses. Cortical ROI definitions will be based on the Human Connectome Project multi-modal parcellation atlas [81]; subcortical ROIs will be based on Freesurfer automated parcellations. ROI analyses will be considered significant at the two-tailed alpha of $p < .05$ after Bonferroni-correction for the number of ROI comparisons. We may also conduct exploratory voxel-level fMRI analyses. These analyses will be corrected for multiple comparisons by applying a voxel-height threshold of $p < .001$, and a cluster-size threshold of $p - \text{FDR} < .05$ to all second-level models.

Grey matter comparisons between Veterans exhibiting STBs and matched controls.

Cortical thickness and grey matter volume (as computed by Freesurfer) will be extracted from the VMPFC and striatum. Measures will be compared between Veterans with STBs and matched controls to test the hypothesis that these metrics are reduced in Veterans with STBs.

Differences in white matter integrity between Veterans with STBs and controls.

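### The imaging power statement calls 0.4 a medium effect, but its N = 72 holds only if 0.4 is Cohen's f, a large effect; at that N a medium effect has about 44% power

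*Combined protocol and SAP*

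**What the plan says.** The power statement is in the participant-groups paragraph of E3.1 (numbered E5.1). It opens "Per power estimations computed with G Power software" and claims "85% power to detect a medium-sized effect of group (0.4) in an ANCOVA model with three groups and two covariates", which "is afforded by a total sample size of 72, or n=24 participants per group". It names neither the effect-size metric nor alpha. It adds that enrolment targets exceed 72 to cover participants who cannot complete everything. E1 and E3.1 set those targets at 30 with attempt, 30 with ideation and 60 controls; E3.1 words them as upper limits.

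Three other places bear on the claim:

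- E2.2.1, the power section for the treatment outcome, describes "0.50 standard deviation units, a medium effect size in Cohen's effect size taxonomy".
- E3.1, MRI Analyses, sets the region-of-interest (ROI) threshold at two-tailed .05 "after Bonferroni-correction for the number of ROI comparisons". E3.2 repeats the rule.
- E3 says that Aim 2 data will be combined with imaging data from protocol #2018-051. It does not say how many participants that adds.

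**The concern.** The document uses the word medium for two different sizes of effect. In E2.2.1 it is half a standard deviation. In E3.1 it is 0.4 on an unnamed scale, and the only usual scale on which 72 participants give 85% power is Cohen's f, where 0.40 is conventionally large.

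This is the only power statement for the group comparisons in E3.1 and E3.2, and brain-based biomarkers are one of the two objectives in section A. A reader who takes the sentence at face value could treat a non-significant ROI contrast as 85%-powered evidence against a medium difference. At the stated N, the three-group test would miss such a difference more often than it would find it.

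**Working it through.** **Inputs.** From E3.1: three groups, two covariates, N = 72 in equal groups, effect 0.4, power 85%. From E1 and E3.1: planned maximum 30/30/60. From E2.2.1: 0.50 SD is medium. Assumed: alpha .05 for the power statement, and f = 0.25 as Cohen's medium. The protocol does not print f = 0.25, but it agrees with 0.50 SD for two equal groups, since f = d/2.

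**Formula.** Noncentral F test with df1 = 2, df2 = N − 3 − 2 and noncentrality λ = N·f². With unequal groups, λ = Σ n_j(μ_j − μ̄)², where μ̄ is the mean weighted by group size and means are in SD units.

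**1. The plan's own figure.** With f = 0.40, λ = 72 × 0.16 = 11.52 and df = 2, 67. Power is **0.853**, and the smallest N reaching 85% is exactly 72. Other readings of 0.4 at N = 72 do not fit:

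| Reading of 0.4 | Power at N = 72 |
|---|---|
| Cohen's f | 85.3% |
| d between extreme groups | 21–27% |
| f² | 99.8% |
| η² | >99.9% |

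Holding f = 0.40, alpha .10 gives 91.6% and alpha .025 gives 77.5%. Using 0 to 3 covariates barely moves the result (85.3–85.4%).

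**2. What f = 0.40 means with three groups.** For evenly spaced means, the extreme difference is f·√6 = 0.40 × 2.449 = **0.98 SD**. If two groups share a mean, it is 3f/√2 = 1.20/1.414 = **0.85 SD**. Conversely, 0.50 SD between extreme groups is f = 0.50/√6 = 0.204 or 0.50 × √2/3 = 0.236.

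**3. Medium effect at N = 72.**
- f = 0.25: λ = 72 × 0.0625 = 4.5; power **44%**. Reaching 85% would take N = 178.
- 0.50 SD between extreme groups: λ = 3.0 (f = 0.204) or 4.0 (f = 0.236); power **31–40%**.

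**4. Medium effect if all 30/30/60 are evaluable** (df = 2, 115). In the f column, means are scaled to f = 0.25 with equal group weights; λ then uses the real group sizes. STB means suicidal thoughts and behaviors.

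| Pattern of means | f = 0.25: λ, power | 0.50 SD: λ, power |
|---|---|---|
| Evenly spaced, controls at one end | 7.73, 69% | 5.16, 51% |
| Both STB groups equally far from controls | 8.44, 73% | 7.50, 68% |
| One STB group differs from the other two groups | 6.33, 60% | 5.63, 54% |
| Controls midway between the STB groups | 5.62, 54% | 3.75, 38% |

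The last pattern belongs in the range. The E3.2 rationale expects high-risk attempters to be less impulsive than healthy controls, and its grey-matter paragraph describes impairment in non-attempters relative to attempters and controls.

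**5. Two-group contrast.** For 60 STB against 60 controls at d = 0.50, λ = 60 × 0.25/2 = 7.5 with df = 1, 116. Power is 0.775, about **78%**.

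**6. Bonferroni.** The plan fixes no number of ROI comparisons. Assuming three (ventromedial prefrontal cortex, orbitofrontal cortex and striatum, the regions named in E3.1), alpha = .05/3 = .0167. At N = 72, f = 0.40 falls to **72%** and f = 0.25 to **28%**.

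**The case against.** The strongest reply is that the calculation itself is correct and the fault lies in one adjective and an unnamed metric. That is true, and it limits the point to labelling.

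Second, 72 is not the planned enrolment. Up to 120 are planned, and much of E3.1 compares all suicidal Veterans with controls, a two-group contrast with about 78% power at a full 60 v 60. So a reader who infers that 44% is the real power of the imaging study goes further than the documents allow: 44% belongs to the three-group test at the N in the power sentence. Equally, 120 is a ceiling and the excess over 72 is explained as cover for loss, so 78% is a best case before Bonferroni.

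Third, pooling with protocol #2018-051 will add participants. The number is not stated and the power sentence does not count them, so the power of the pooled analysis cannot be worked out from the documents. This calls for a caveat and does not rescue the sentence.

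Fourth, covariates add precision. Bringing f = 0.25 to about 85% at N = 72 would require them to explain about 60% of within-group variance, and the plan assumes no such figure.

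Fifth, A5 lists the baseline group difference as exploratory, and the imaging hypothesis in A2 (symptom reduction correlated with change in brain function) is a different analysis. This stands and lowers the priority, although E3.1 does present its ROI tests as primary hypothesis testing.

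Last, nothing in the plan says that a null result will be read as absence of a medium effect. E3.1 says only that other circuits or data-driven methods could then be explored. The misreading is a risk that the wording creates; the plan does not commit to it.

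**Conclusion.** The point holds as a mislabelled effect size, and it should be fixed. The plan has 85% power at N = 72 for a large effect. For a medium one, the three-group test has 44% power at that N (f = 0.25), or 31–40% on the benchmark in E2.2.1. With all 30/30/60 evaluable the ranges are about 54–73% and 38–68%, and the 60 v 60 contrast has about 78% for 0.50 SD. None of the participant numbers stated in the plan gives 85% for a medium effect.

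These figures assume an unadjusted alpha of .05, f = 0.25 as medium, no variance explained by covariates, and no pooled participants. The Bonferroni figures further assume three ROI tests. The documents do not support the inference that the software calculation was wrong, that enrolment must rise to 178, or that the treatment comparison is affected: the basis for 130 randomised participants in E1 and E2.2.1 is separate.

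**What to change.** Reword the power sentence in E3.1:

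- Name the metric as Cohen's f, state alpha, and describe f = 0.40 as large (extreme groups 0.85–0.98 SD apart).
- Add power for a medium effect at 72 and at 30/30/60, for both the three-group test and the STB-versus-control contrast. State how many ROI tests are assumed and give the power after Bonferroni correction.
- Say that these figures exclude participants pooled from protocol #2018-051, or give the number and include them.
- State in E3.1 and E3.2 that non-significant ROI contrasts will be reported with confidence intervals and will not be taken as evidence against a medium effect.

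The cost is a wording change and a less favourable printed figure. Enrolment, procedures and the randomised comparison stay as they are.

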Behavioral Data Analysis:

NIH Toolbox Dimensional Change Card Sort Task: Accuracy and reaction time scores will be computed for each subject (both raw and age-adjusted); higher accuracy and lower reaction times are associated with greater cognitive flexibility. Subject-specific scores will be entered into MATLAB ANCOVA models testing group differences.

NIH Toolbox Flanker Inhibitory Control and Attention Test: Total winnings and the ratio of high vs. low risk gambles will be entered into MATLAB ANCOVA models testing group differences.

MRI Analyses: Analyses for primary hypothesis testing will employ a region of interest (ROI) approach. ROIs in the cognitive control areas of ventrolateral PFC (VLPFC- pars orbitalis, pars triangularis, pars opercularis), dorsolateral PFC (DLPFC-approx. Brodmann's Areas 46/9), and anterior cingulate (ACC-rostral and dorsal) will be used in structural and functional neuroimaging analyses. Striatal ROIs will also be tested as they are part of thalamo-cortical loops that include control regions [89]. Cortical ROI definitions will be based on the Human Connectome Project multi-modal parcellation atlas [90]; subcortical ROIs will be based on Freesurfer automated parcellations. ROI analyses will be considered significant at the two-tailed alpha of $p < .05$ after Bonferroni-correction for the number of ROI comparisons. We may also conduct exploratory voxel-level fMRI analyses. These analyses will be corrected for multiple comparisons by applying a voxel-height threshold of $p < .001$, and a cluster-size threshold of $p - FDR < .05$ to all second-level models.

Grey matter comparisons between groups. Anatomical differences in cognitive control regions may contribute to poor cognitive control and the decision-making impairments observed in non-attempters relative to attempters and controls. As a test of this hypothesis, cortical thickness and grey matter volume in cognitive control regions (extracted with Freesurfer) will be compared between high-risk Veterans with STBs, low-risk Veterans with STBs, and controls. Morphometry statistics will be entered into GLM group contrasts for each ROI.

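### The imaging power figure (85% at N = 72) holds for one uncorrected test; under the Bonferroni rule set for the ROI tests, three-group power at that N is about 72% for three regions

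*Combined protocol and SAP*

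**What the plan says.** The power statement is in section E3.1, in the paragraph on participant groups (numbered E5.1 in the text). It says that "85% power to detect a medium-sized effect of group (0.4) in an ANCOVA model with three groups and two covariates is afforded by a total", and the number it then gives is a "total sample size of 72, or n=24 participants per group". The source is given as "Per power estimations computed with G Power software". It states no alpha and no allowance for multiple tests. The next sentence explains enrolment above this number solely by participants who cannot complete every part of the study. The imaging target is 120: up to 30 with an attempt, up to 30 with ideation and up to 60 controls (E1, E3.1).

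The MRI Analyses paragraph of E3.1 makes ROI analyses the vehicle for primary hypothesis testing, names three regions (VMPFC, orbitofrontal cortex, striatum) and sets the rule: "ROI analyses will be considered significant at the two-tailed alpha of $p < .05$ after Bonferroni-correction for the number of ROI comparisons". E3.2 repeats the rule for a longer list that begins "ROIs in the cognitive control areas of ventrolateral PFC (VLPFC- pars orbitalis, pars triangularis, pars opercularis), dorsolateral PFC" and continues with rostral and dorsal anterior cingulate and the striatum. That is seven named regions. E3.2 has no power statement.

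**The concern.** The power figure and the decision rule sit in the same section but use different alphas. A sample size that gives 85% power at .05 gives less at .05/2 or .05/3. The plan treats 72 completers as enough and assigns the whole difference between 72 and 120 to loss. If the ROI tests need more than 72 completers under their own rule, part of that difference is already spent. A null ROI result from about 72 completers would also be credited with more power than it had.

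**Working it through.** **Inputs.** From E3.1: f = 0.4 (read as Cohen's f, the scale G*Power uses for an ANCOVA group effect), three groups, two covariates, N = 72 in equal groups. From the MRI Analyses paragraphs: .05 divided by the number of ROI comparisons, m.

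**Formula.** Noncentral F with df1 = 3 − 1 = 2, df2 = N − 3 − 2, noncentrality λ = f² × N. Power is the probability that this variable exceeds the central-F critical value at .05/m. At N = 72, df2 = 67 and λ = 0.16 × 72 = 11.52.

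**The plan's own figure.** At alpha .05 the critical F is 3.13 and power is 85.3%. N = 71 gives 84.8%, so 72 is the smallest N that reaches 85%. This is why alpha is inferred to be an uncorrected .05; at .05/2 the figure already fails.

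**Under the Bonferroni rule, three-group test:**

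| ROI comparisons | alpha | critical F (N = 72) | power, N = 72 | power, N = 120 (λ = 0.16 × 120 = 19.2) |
|---|---|---|---|---|
| 1 | .05 | 3.13 | 85.3% | 97.9% |
| 2 (VMPFC, striatum) | .025 | 3.90 | 77.5% | 95.9% |
| 3 (E3.1 list) | .0167 | 4.36 | 72.4% | 94.4% |
| 7 (E3.2 list) | .0071 | 5.32 | 61.2% | 90.0% |

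A third covariate (intracranial volume, in the morphometry models) lowers power at N = 72 by less than 0.1 percentage point. If each of the seven regions were split by hemisphere, which is an assumption, 14 comparisons would give 52.0% at N = 72.

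**Unequal groups at N = 120.** The last column takes f as defined on the actual group weights. If f = 0.4 is instead defined on equally weighted means, then with 30/30/60 λ = Σ nⱼ(μⱼ − weighted mean)² depends on the pattern of means:

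- Controls differ from both suicidal subgroups: λ = 21.6, power 96.7% (m = 3) and 93.8% (m = 7).
- One suicidal subgroup differs from the other two groups: λ = 16.2, power 89.3% and 82.6%.
- Controls midway between the two subgroups: means −0.49, +0.49 and 0, λ = 2 × 30 × 0.24 = 14.4, power 84.6% and 76.4%.

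**Two-group reading.** Several E3.1 contrasts compare Veterans with suicidal thoughts or behaviors against controls. If f = 0.4 is carried to a 1-df contrast with equal groups (an assumption), power at N = 72 is 86.2% for m = 2 and 82.3% for m = 3.

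**The case against.** Several objections have force.

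- **No printed number is wrong.** The 85% reproduces, and the sentence does not say that it covers the ROI tests. The behavioral ANCOVAs, which use age and sex as covariates and carry no Bonferroni rule, do have that power. This stands: the fault is unstated scope. But it is the only power statement for the imaging aim, and the same section calls the ROI analyses its primary tests.
- **The size depends on the contrast and the count.** The plan does not define how ROI comparisons are counted, and some E3.1 tests use two regions and two groups. On that reading power at 72 is about 86%, so the shortfall disappears; with three regions it is about 82%. The 72% therefore belongs to the three-group test that the power statement itself specifies.
- **E3.2 makes no power claim.** The 61% is an extension. E3.2 draws on the same groups and its grey-matter analysis compares all three, but its tractography contrast is attempt versus ideation only.
- **72 is a minimum, and data will be pooled.** Aim 2 data are to be combined with protocol #2018-051, but no number is given and the 72 does not rely on it.
- **Status.** A5 lists the brain-behavior hypotheses as exploratory. That limits the weight of the point but does not make the power figure match the decision rule.

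A reader might infer that the imaging study is underpowered as planned. The documents do not support this: at 120, three-region power is about 94% on the actual group weights and about 85% even under the least favorable pattern of means above. A reader might also take the equal-group solutions for 85% power, 92 completers for three regions and 108 for seven, and conclude that tolerable loss falls from 40% to 23% or 10%. Those figures do not fit the design. Equal groups would mean 31 and 36 per group, above the cap of 30 in each suicidal subgroup.

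**Conclusion.** The point holds in limited form. The 85% at N = 72 describes one uncorrected three-group test. Under the plan's own Bonferroni rule, three-group power at that N is about 77% for two regions and about 72% for the three named in E3.1, and about 61% if the calculation is extended to the seven named in E3.2. These figures rest on f = 0.4, equal groups of 24, two covariates and an inferred alpha of .05 behind the printed figure.

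The consequence is narrow. For the three-group ROI tests 72 completers is not a sufficient floor, so the excess over 72 cannot all be set aside for loss. How much can be set aside depends on the allocation, the contrast and the ROI count, and the plan fixes only the allocation. It gives no expected loss rate for imaging completers, so nothing shows that the analysis will end near 72. The point concerns the stated power and the loss allowance; it gives no ground for changing the enrolment target.

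**What to change.** In the participant-groups paragraph of E3.1:

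1. State that 85% at N = 72 applies to one test at an uncorrected .05, such as each behavioral ANCOVA.
2. State how ROI comparisons are counted, the resulting number and the corrected alpha.
3. Give the ROI power at N = 72 on that basis: 72% for three regions with the three-group test. If E3.2 is to rely on the same calculation, say so and give its figure.
4. Recompute the completers needed for 85%, and from that the loss allowance out of 120, under the planned 30/30/60 allocation and for the contrast actually tested (three groups, or suicidal versus control). State how f is defined when groups are unequal. Do not insert the equal-group values of 92 and 108.

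The cost is a short rewording and one recalculation. Enrolment and procedures do not change; the only downside is a less favorable stated power for the ROI tests.
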